15.5 Quality of life assessments: Instructions for administration

a. Administration of questionnaires

1. All questionnaires should be completed prior to the visit with the physician. The time the questionnaire is completed and the time of the physician visit should be documented.
2. The first time the patient completes the questionnaires: Please read to the patient the instructions attached to each patient questionnaire. Explain the specific administration times for this protocol. Patients should be directed to report all symptoms and limitations whether or not they are related to the cancer or its treatment.
3. It is permissible to assist patients with completing the questionnaires being careful not to influence the patient's response. Note on the **S1404** Cover Sheet for Patient-Completed Questionnaires what assistance was required and indicate reason (e.g., elderly, too sick, etc.). Discourage family members from: 1) being present while the patient completes the questionnaire and/or 2) influencing patient responses to the questions.
4. It is very important to review the questionnaires after the patient has completed them to be sure all of the questions have been answered and that only one answer is marked. If the patient has marked more than one answer per question, ask the patient which answer reflects how she is feeling. If the patient has skipped a question, tell the patient that a question was not answered and ask if she would like to answer the question. Always give the patient the option to refuse. Indicate on the form by the question that the patient did not want to answer this question.
5. If a patient refuses or cannot complete the questionnaire for some reason, this must be documented on the **S1404** Cover Sheet for Patient Completed Questionnaires and submitted (see [Section 14.4h](#)).
6. Questionnaires must be completed by the patient at disease recurrence. On-treatment questionnaires may be submitted in place of recurrence questionnaires if:
 - The patient has already completed the on-treatment questionnaires, AND
 - The patient was aware of recurrence prior to completing the on-treatment questionnaires, AND
 - The patient did not receive any treatment after completing the on-treatment questionnaires.

Otherwise, separate recurrence questionnaires must be completed by the patient and submitted by the study site.

b. Additional quality control procedures:

When a patient is registered on **S1404**, a calendar should be made with dates of upcoming patient-completed questionnaires noted. A copy of this calendar can be given to the patient with the notation that the questionnaires should be completed. You may wish to photocopy the Study Calendar, [Section 9.0](#), and include the patient's name and specific dates. A copy of this should be kept in the patient file.

If a patient refuses or cannot complete the patient questionnaires at one time point, **he or she should be asked to do so at the next scheduled assessment** time. Submit the **S1404** Cover Sheet for Patient-Completed Questionnaires documenting the reason why the questionnaires were not done.

Anyone involved in the collection of quality of life data in SWOG trials should review the training program available on the SWOG website accessible from three

locations. On the SWOG Home Page (prior to member login), in the QUICKLINKS section on the bottom right corner of the page, there is a link to the Patient Reported Outcomes Training. The other two locations that the training is available are after SWOG member login on the CRA Workbench. The Training section and the New CRAs! section both contain access to the Patient Reported Outcomes (PROs) training module. The training program is a narrated set of slides designed to standardize the way quality of life data is collected from patients. Questions regarding the quality of life assessments can be addressed to the SWOG Data Operations Office ([name]).

c. **S1404** Cover Sheet for Patient-Completed Questionnaires

For each time point that the FACT-BRM, EQ-5D-3L, and FACIT-D are administered, the nurse or CRA completes the **S1404** Cover Sheet for Patient-Completed Questionnaires. The Cover Sheet is submitted with the set of patient-completed forms at each scheduled assessment. The Cover Sheet is very important for tracking how and when the patient forms were completed. When a patient-completed form is not administered at a scheduled time point, it is important to know why the assessment did not occur; the form includes potential reasons for a patient not completing a form. See [Section 14.4g](#) for data submission guidelines.

d. QOL Questionnaire Administration Schedule

The FACT-BRM, EQ-5D-3L, and FACIT-D are scheduled to be administered at the following time points:

- Prior to Cycle 1
- Week 4 of the first cycle of treatment
- Prior to Cycles 3, 4, 5 and 6
- Week 24 after the date of last treatment
- Week 48 after the date of last treatment
- Relapse

Patients who relapse before 48 weeks after date of last treatment will complete a questionnaire at relapse. Patients do not need to complete any further questionnaires after relapse. Patients who go off protocol therapy before Week 49 (Cycle 6) without recurrence will complete the two post-treatment questionnaires (at 24 and 48 weeks from the date of last treatment).

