- i. Women of child bearing potential must have a negative serum or urine pregnancy test at screening within 28 days prior to registration. Following randomization, serum or urine pregnancy tests are required within 72 hours prior to the first dose of study treatment, then according to institutional practice during therapy, tests should coincide with clinic visits for blood work and ending with the discontinuation of study treatment. At discontinuation, a negative pregnancy test within the preceding 6 weeks is sufficient. A pregnancy test should be done at any time there are clinical concerns for possible pregnancy.
- j. Patients with primary melanoma of the head and neck or unknown primary with disease in the axilla will also require a neck CT.
- k. Disease assessments by PET-CT or CT chest/abdomen/pelvis (or MRI if CT cannot be done), and neck CT as needed will be performed every 12 weeks (-/+ 2 weeks) until 2 years from randomization, then every 6 months (+/- 4 weeks) until 5 years from randomization, then follow for survival. The same imaging modality as used at prestudy for disease assessment should be used throughout the trial. During treatment and follow-up, brain MRI/CT or other imaging studies must be repeated annually (+/- 4 weeks). For PET-CT imaging, iodinated contrast is recommended in addition to FDG for optimal relapse detection. If there is a contra-indication to iodine, non-contrast chest CT and MRI of abdomen/pelvis with gadolinium are acceptable body imaging alternatives. If there is a gadolinium allergy, or MRI brain intolerable for the patient, CT with iodinated IV contrast is adequate brain imaging. MRI of the brain is required for patients with progressive disease.
- l. Slides must be submitted as described in [Section 15.2](#). Patients cannot be randomized on Step 2 until e-mail confirmation has been received indicating that the specimen was adequate for determining PD-L1 status.
- m. If patient consents, submit specimens for banking as specified in [Section 15.0](#).
- n. Blood needs to be drawn prior to treatment.
- o. Submit scans as outlined in [Sections 14.0](#) and [15.0](#).
- p. Cover Sheet, FACT-BRM, EQ-5D-3L and FACIT-D should be completed 24 weeks (± 2 weeks) and 48 weeks (± 2 weeks) after the date of last treatment.

q. If relapse occurs before 48 weeks after date of last treatment, Cover Sheet, FACT-BRM, EQ-5D-3L and FACIT-D should be completed at the time of relapse.

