The EQ-5D-3L has two systems. The descriptive system measures three functional domains (mobility, self-care, usual activities) and two symptom domains (pain/discomfort and anxiety/depression). Each domain has three levels (no problems, some problems, extreme problems). A visual analog system (VAS) records self-rated global health between “best imaginable health state” and “worst imaginable health state” and can be used as a quantitative measure of health outcome as judged by individual patients. The three functional and two symptom domains can be summarized categorically, and the VAS global health rating can be summarized quantitatively. The measures can then be combined into a single summary index. Utility scoring will follow the US and European algorithms.

c. **Endpoints:** PRO endpoints are measured by the FACT-BRM, FACIT-D, and EQ-5D-3L. These endpoints are affected by both disease progression and treatment tolerability.

The Trial Outcome Index (TOI) from FACT-BRM is the primary PRO endpoint for this study. The TOI combines four subscales: Physical Well-Being, Functional Well-Being, the BRM Physical Subscale, and the BRM Cognitive/Emotional Subscale. The primary TOI endpoint will be the TOI score at Cycle 3.

Secondary PRO endpoints from the FACT-BRM are the six individual FACT-BRM subscales and the FACT-BRM total score. Secondary PRO endpoints from the FACIT-D are symptom-specific subscale and specific items and the FACIT-D total score. Secondary PRO endpoints from the EQ-5D-3L include the summary index as well as each of the six individual EQ-5D-3L domains.

For PRO endpoints, the baseline score will be accounted for as a covariate in multivariable regression models. The change between the baseline and Cycle 3 scores will also be examined as a sensitivity analysis. In addition, the changes over all time points in the TOI endpoint as well as all of the secondary PRO endpoints will be analyzed using longitudinal data analytic approaches described below.

d. Schedule for PRO data collection:

Table 11.8.1 PRO Data Collection Schedule

Treatment Cycle	Baseline	Cycle 1	Cycle 3	Cycle 5	Cycle 7	Cycle 9	Follow-up	Recurrence
Study Time*	Before first day of treatment	4 weeks	13 weeks	25 weeks	37 weeks	49 weeks	24 and 48 weeks after protocol treatment discontinuation	See below (a, b)

* assuming no treatment delays

a) Once patient has disease recurrence, no subsequent PRO data will be collected.

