 b) If recurrence occurs more than 48 weeks after protocol discontinuation, then PRO data collection at the time of recurrence is not required.

With the exception of the recurrence time point, at each time point the FACT-BRM, FACIT-D, and EQ-5D-3L will be administered prior to all other study procedures. At the time of recurrence, the FACT-BRM, FACIT-D, and EQ-5D-3L will be administered after the patient sees the treating investigator. At each time point, if

a patient does not complete one or both PRO instruments, the site staff will record the reason on the PRO Coversheet from predefined choices.

e. **Analysis Populations:** The primary analysis population will be based on an intent-to-treat (ITT) approach, incorporating data from all eligible randomized patients. To be evaluable, patients must have completed both the baseline and the Cycle 3 assessments.

f. PRO instrument completion and compliance:

The completion rate for the primary endpoint is defined as the number of patients who complete a sufficient number of items to score the FACT-BRM TOI according to the missing data rules for the instrument, divided by the number of eligible randomized patients at each time point. The completion rate is expected to decrease over time because some patients will not complete all protocol therapy and some patients will have disease recurrence or die.

The compliance rate for the primary endpoint is defined as the number of patients who complete a sufficient number of items to score the FACT BRM TOI according to the missing data rules for the instrument, divided by the number of patients who were expected to complete the PRO instrument. The denominator of the compliance rate will not include patients who have died, recurred, or went off protocol therapy prior to that time point, or could not complete an instrument due to language translation not being available.

The completion and compliance rates of the other subscales and total scores will be defined in a similar fashion. Completion and compliance rates by instrument, visit, and treatment arm will be described.

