We do not have preliminary PRO data on the FACT-BRM TOI with pembrolizumab or IFN in this particular patient population (the trial has wider eligibility than prior trials). The follow-up standard deviation for the FACT-BRM TOI was 20 in a set of nearly 200 patients receiving IFN for renal cell carcinoma. (31) This is consistent with data from Trask et al. (2004) in a small series of patients receiving IFN for high risk melanoma. (32) Thus we assume a cycle 3 standard deviation of the FACT BRM TOI of 20, common between both arms. Using Yost (2005), the estimated minimally important difference for the FACT BRM TOI is 5-8 points. If the standard deviation is 20 points, this difference is consistent with clinically meaningful effect sizes of 0.25-0.33, using distribution-based methods and anchor-based methods, respectively, identified by Yost et al. (33) Given the sample size is large, power is based on identifying a small effect size of 0.25. It is assumed, conservatively, that with a median OS for non-long term survivors of 3.96 and a median RFS for non-long term survivors of 1.44 years, then by cycle 3, 5% of patients will drop out due to death, 12% due to worsening disease, and 3% for other reasons, producing an overall dropout rate of 20% at cycle 3. Further, an additional 10% patients are assumed to be non-adherent. Patients who drop out or are non-adherent are considered invaluable. Note that in power calculations, the 10% non-adherence rate reduces the nominal effect size by 10% (to 0.225), while the 20% dropout rate inflates the estimated sample size by a factor of $1/(1-0.2)$ or 25%. Using a 2-sided alpha=0.05 test and a two-arm normal design, and accounting for dropout and non-adherence as specified, there will be 94% power to detect the effect size difference of 0.25 between the two arms.

Power will be worse with a smaller sample size. For instance, a sample size of 260 patients (130 per arm) will provide 83% power for a notably higher standardized difference (difference between means / standard deviation) of 0.4, using the same parameters as specified above. This effect size corresponds to a minimally important difference of 8 points in the FACT BRM TOI at cycle 3 if the standard deviation is 20%, the upper limit of the range of the minimally important difference as indicated in Yost et al.

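### The primary PRO analysis is labelled intent-to-treat, but the form schedule and evaluability rule restrict it to patients still on protocol therapy at about Week 13

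*Combined protocol and SAP*

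**What the plan says.** Section 11.8c sets the endpoint: "The primary TOI endpoint will be the TOI score at Cycle 3". Table 11.8.1 places that form at 13 weeks. Section 11.8e states: "The primary analysis population will be based on an intent-to-treat (ITT) approach, incorporating data from all eligible randomized patients". The sentence after it adds: "To be evaluable, patients must have completed both the baseline and the Cycle 3 assessments". Section 11.8h also says that PRO data are collected and analysed for everyone on the trial rather than for a subset.

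The collection rules are narrower. Section 15.5d schedules the on-study forms by cycle (before Cycle 1, Week 4, then before Cycles 3, 4, 5 and 6). For early stoppers it says: "Patients who go off protocol therapy before Week 49 (Cycle 6) without recurrence will complete the two post-treatment questionnaires". Table 11.8.1 gives the follow-up forms as "24 and 48 weeks after protocol treatment discontinuation". Footnote p of calendar 9.1 says the "FACT-BRM, EQ-5D-3L and FACIT-D should be completed 24 weeks" and again 48 weeks after the last treatment, each within 2 weeks; calendars 9.2 and 9.3 carry the same footnote. Section 11.8f leaves out of the compliance denominator patients who died, recurred or "went off protocol therapy prior to that time point".

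For power, section 11.8h assumes loss by Cycle 3 of 5% from death, "12% due to worsening disease, and 3% for other reasons", plus a further 10% non-adherent. It makes no distinction by arm.

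**The concern.** The TOI is meant to capture how patients feel under treatment, and section 11.8c acknowledges that PRO endpoints are affected by tolerability. If the Week 13 form is scheduled only for patients still on protocol therapy, whether a patient contributes depends on a post-randomization event related to the outcome. Randomization then no longer protects the comparison, and the intent-to-treat label tells the reader otherwise.

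There is reason to expect the loss to differ by arm. In section 8.3, ipilimumab-related diarrhea or colitis of Grade 2 or more leads to permanent discontinuation. In Table 1 of section 8.4, Grade 2 or 3 leads to withholding of pembrolizumab. No comment on those rules is intended. Their consequence for the PRO data is that the same symptom can end Week 13 collection in one arm and not in the other. What is at stake is the interpretation of the main quality-of-life comparison. OS and RFS are untouched.

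**Working it through.** **1. The plan's own power figure.** Inputs from sections 11.1 and 11.8h: 1,240 eligible patients randomized 1:1, 20% dropout, effect 0.25 SD reduced by 10% to 0.225, two-sided alpha 0.05.
- Evaluable per arm: 1,240 × 0.8 / 2 = 496.
- SE in SD units: √(2/496) = 0.0635.
- Power: Φ(0.225/0.0635 − 1.96) = Φ(1.58) = 94.3%. The stated 94% is reproduced.

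**2. Can an early stopper have a Week 13 score?** With the last dose in Week L, the first post-treatment form falls in Weeks L + 22 to L + 26.

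| Last dose | First post-treatment form |
|---|---|
| Week 1 | Weeks 23–27 |
| Week 4 | Weeks 26–30 |
| Week 7 | Weeks 29–33 |
| Week 10 | Weeks 32–36 |

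Week 13 ± 2 is Weeks 11–15, so none of these can serve. No single sentence forbids a Week 13 form for these patients. Its absence follows from sections 15.5d and 11.8f and the calendar footnotes read together.

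**3. The analysis window.** Section 11.8g allows ± 2 weeks around the completion of cycle 3, whereas Table 11.8.1 and section 15.5d put the form at its start. With the 12-week cycles of section 14.4f, completion is about Week 25 (window Weeks 23–27). Read literally, a post-treatment form after a last dose in Weeks 1–5 could then count as the Cycle 3 score. Table 11.8.1 numbers cycles differently (Cycle 5 at 25 weeks, Cycle 7 at 37), which implies 6-week cycles and completion at about Week 19. Neither reading gives Week 13.

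**4. Possible size of the bias.** Let s be the proportion of otherwise evaluable patients in each arm who stop before Week 13, and g the points by which stoppers would score below completers (taken as equal in both arms). Each arm's full mean is its completer mean minus s × g. The completer difference therefore departs from the full difference by g × (s_control − s_pembrolizumab). The documents give neither s nor g; the values below are assumptions.
- 10% versus 3%, g = 10: 10 × 0.07 = 0.7 points.
- 20% versus 5%, g = 10: 10 × 0.15 = 1.5 points.
- The target is 0.25 × 20 = 5 points, so these are 14% and 30% of it.
- If the stop rates are instead counted as shares of all randomized patients on top of the 20% dropout, divide by 0.8: 0.9 and 1.9 points.
- If stoppers have recovered and score better, g is negative and the shift has the same size away from the null.

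**5. Effect on power through numbers alone.** Further losses of 10%/3% leave 434 versus 477 evaluable and 92% power; 20%/5% leave 372 versus 465 and 90%. Collecting the missing forms would give 94.3% (dropout still 20%) to 95.0% (dropout 17%, if all of the 3% for other reasons is recovered). The issue is bias, not power.

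**The case against.** Several stronger readings are tempting, and the documents do not support them.

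- **A reader might infer that the attrition allowance leaves almost nothing for toxicity stops.** Section 11.8h adds 10% non-adherence, also treated as inevaluable, to the 20%. The 17% for death and worsening disease is called conservative, and it is: the RFS models in section 11.3 give relapse or death by Week 13 of 0.65 × (1 − exp(−0.67 × 0.25)) = 10.0% for control and 0.59 × (1 − exp(−0.48 × 0.25)) = 6.7% for pembrolizumab. There is room in the total. What remains true is that there is no item for toxicity stops and no difference by arm.
- **A reader might infer that the bias must run towards no difference, and that the plan concedes this.** Section 11.8g argues that dropout from worsening health or death would be conservative, then says the pattern cannot be assumed. Patients off a toxic drug may have recovered by Week 13.
- **A reader might take the Grade 3/4 toxicity rates in section 2.0 (64%, 43%, 12%) as stop rates.** They come from different trials and are incidences, not discontinuations by Week 13. The in-trial Grade 3–4 irAE rates in Appendix 18.8 (35% ipilimumab, 15% pembrolizumab) are not stop rates either.
- **A reader might say only patients tolerating therapy are compared.** Patients with held, skipped or reduced doses can stay on protocol; section 7.4 removes for delay only after more than 84 consecutive days.

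The plan also has safeguards: mixed models on all available scores, a comparison of evaluable with inevaluable patients, and pattern-mixture models with a pattern for living, recurrence-free patients who do not complete therapy. These count in its favour. But the mixed model is a consistency check, the pattern-mixture model runs only if non-random dropout is found, and neither supplies the missing Week 13 scores. Finally, QOL is an additional objective (section 1.3), which limits the weight of the point.

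**Conclusion.** The point holds in a limited form. The schedule, the compliance definition and the evaluability rule together make the primary PRO regression a comparison of recurrence-free patients still on protocol therapy at about Week 13. That contradicts the intent-to-treat label in section 11.8e and the all-patients statement in section 11.8h. Because stopping for toxicity is likely to differ by arm, the contrast can be biased, in a direction the documents do not settle. An illustrative 0.7 to 1.5 points against a 5-point target rests on assumed stop rates and an assumed 10-point gap. Power stays at 90% or above in those scenarios if only lost numbers are counted. This is a cheap improvement to an additional objective, with no bearing on OS or RFS.

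**What to change.** **If Week 13 forms can still be collected:** in sections 11.8d and 15.5d and the three calendars, schedule the Week 13 questionnaire by weeks from randomization for every living, recurrence-free patient, whatever the treatment status. In section 11.8f, drop being off protocol therapy as an exclusion from the compliance denominator at that time point. The cost is one extra questionnaire for off-treatment patients, who already attend visits 6 and 12 weeks after the last dose and imaging every 12 weeks. It would be more if later time points were added.

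**If collection is complete,** as the November 2023 version date and the past-tense enrolment and toxicity figures in Appendix 18.8 suggest:
- describe the primary regression as an analysis of on-protocol completers, not intent-to-treat;
- report missing Week 13 forms by reason and arm;
- make two sensitivity analyses unconditional: the mixed-model Week 13 contrast using all patients with any PRO form, and the pattern-mixture analysis with the off-therapy pattern. The mixed model still assumes missing at random.

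This costs SAP wording and two analyses the plan already outlines.

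**In either case,** reconcile the window around the completion of cycle 3 (section 11.8g) with the 13-week time point in Table 11.8.1 and the pre-Cycle 3 form in section 15.5d, and use one cycle numbering throughout.
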